### 5.2 Variables Used for Stratification of Randomization

No stratified randomization is planned. This is an open-label study.

## 6.0 Analysis Conventions

### 6.1 Definition of Baseline

The last non-missing measure collected on or before the day of the first dose of study drug injection in Study 1311.5 for each randomized subject will be used as the Baseline for summary of demographics, disease characteristics and safety analyses. For efficacy endpoints except modified total Sharp score (mTSS), the baseline is defined as the last non missing pre-treatment observation prior to first dose in Study 1311.5. The Baselines for mTSS are defined as the last non-missing observation prior to Day 13 and closest to Day 1 in Study 1311.5.

For mTSS, data for Week 24 in Study 1311.5 and Week 24 in Study M16-244 are considered in analyses. In the context of visits corresponding to mTSS data collection

they will be referred to as Week 24 (Study 1311.5) and Week 24 (Study M16-244) respectively.

If multiple measurements are recorded on the same day, the worst of the multiple measurements will be used.

## **6.2                   Definition of Final Observation (Applicable to Safety Analyses Other than Laboratory and Vital Signs)**

Final observation is defined as the last non-missing observation collected within 140 days (20 weeks) following the last dose of study drug.

## **6.3                   Definition of Rx Days (Days Relative to the First Dose of Study Drug)**

Rx days are calculated for each time point relative to the date of first dose of study drug. They are defined as the number of days between the date of the first dose of study drug and the specific time point. Rx days are negative values when the time point of interest is prior to the first study drug dose day. Rx days are positive values when the time point of interest is on or after the first study drug dose day. The day of the first dose of study drug is defined as Rx Day 1, while the day prior to the first study drug dose is defined as Rx Day –1 (there is no Rx Day 0).

## **6.4                   Definition of Analysis Windows**

All time points and corresponding time windows are defined based on Rx Days.

For efficacy analyses, laboratory parameters, and vital sign variables, analysis windows are constructed using the following algorithm:

- Determine the nominal Rx day for each visit (e.g., Week 4 [4 weeks after Baseline visit] equals Rx Day 29).
- In order to include all post baseline data, the first post-baseline interval starts on the first day after the first dose of study drug (Rx Day 2).

---

- Determine the window around a specific nominal Rx day by adding or subtracting half of the interval between adjacent visits (e.g., days between Week 2 and Week 4 is 14). The threshold between adjacent visits is determined by splitting the interval evenly between the visits. If the resulting split is between Rx days, then the threshold is determined as the midpoint between the adjacent visits. If the resulting split is on a Rx day, then the threshold is determined as being between that Rx day and the Rx day prior to it (e.g., the split between Week 2 and Week 4 would be between Rx Days 22 and 23).
- If more than one assessment is included in a time window the assessment closest to the nominal day will be used. If there are two observations equidistant to the nominal day, the one after the nominal day will be used in analyses. If more than one assessment is included on the same day, then the worst assessment on that day will be used in analyses. For laboratory values, if there are multiple measurements on the same day, average value will be used.

The protocol specified visits and corresponding time windows used in the various efficacy analyses, laboratory parameters, and vital sign variables, are presented in the following tables.

**Table 1. Analysis Windows for Efficacy Variables (PtGA, Patient's Assessment of PsA Pain Intensity, HAQ-DI, SF-36v2, TJC68, SJC66, PASI, BSA, sPGA, PhGA, hsCRP for DAS)**

Protocol Specified Visit Week	Lower Bound	Target Day	Upper Bound
0	1	1	1
4	2	29	57
12	58	85	127
24	128	169	211
36	212	253	295
48	296	337	351
52	352	365	378

**Table 2. Analysis Windows for BASDAI**

Protocol Specified Visit Week	Lower Bound	Target Day	Upper Bound
0	1	1	1
24	2	169	211
36	212	253	295
48	296	337	351
52	352	365	378

**Table 3. Analysis Windows for FACIT-FATIGUE**

Protocol Specified Visit Week	Lower Bound	Target Day	Upper Bound
0	1	1	1
24	2	169	211
36	212	253	295
48	296	337	378

**Table 4. Analysis Windows for LDI, LEI, SPARCC, mNAPSI During the Open Label Treatment Period**

Protocol Specified Visit Week	Lower Bound	Target Day	Upper Bound
0	1	1	1
12	2	85	127
24	128	169	211
36	212	253	295
48	296	337	351
52	352	365	378

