5.0 Investigational Plan

5.1 Overall Study Design and Plan: Description

This is a 52-week multicenter, single-arm, OLE study to assess safety, tolerability and efficacy of risankizumab in PsA subjects who have completed all doses of study drug and the Week 24 visit of Study 1311.5 (Phase 2 randomized clinical trial in PsA subjects, sponsored by Boehringer Ingelheim).

Subjects who complete all doses of study drug and the Week 24 visit in Study 1311.5, meet all inclusion criteria (Section [5.2.1](#)) and none of the exclusion criteria (Section [5.2.2](#)) have the option to sign the informed consent form and enter the OLE study, receiving risankizumab 150 mg administered every 12 weeks with an additional dose of risankizumab made available at the Week 4 visit for those subjects that have not achieved a protocol defined response (defined as an improvement in tender and swollen joint count of $\geq 20\%$ compared with the baseline in Study 1311.5), provided the investigator believes this may be beneficial to the subject.

If the Study M16-244 Week 0 visit occurs on the same day or in the 4 days following the Study 1311.5 Week 24 visit only selected activities are required as some activities are common to both studies and are not required twice. See Study Activity Table in [Appendix C](#). If the OLE Week 0 visit occurs > 4 days and ≤ 8 weeks after the Study 1311.5 Week 24 visit, all procedures specified in [Appendix C](#) at Week 0 visit are required.

Subjects that enroll in the OLE study are no longer enrolled in Study 1311.5 and will not complete the Week 28 or Week 32 visits in Study 1311.5.

Subjects who are not enrolled in Study M16-244 within 8 weeks of the Study 1311.5 Week 24 visit are not eligible to participate in Study M16-244.

The study is anticipated to enroll up to 180 subjects. Study visits will occur at Week 0/Enrollment, Weeks 4, 12, 24, 36, 48 and 52. A \pm 4 day window is permitted around scheduled study visits after enrollment.

36-Week Treatment Period

[figure not shown]

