5.3.3.3 Further Endpoint(s)

Further efficacy endpoints will include, but are not limited to, the following:

- ACR 50 at all measured time points
- ACR 70 at all measured time points
- Change in Tender Joint Count at all measured time points as compared to baseline
- Change in Swollen Joint Count at all measured time points as compared to baseline
- Change in HAQ-DI at all measured time points as compared to baseline
- Change in SF-36 at all measured time points as compared to baseline

- Change in Dactylitis count at all measured time points as compared to baseline
- Change in SPARCC Enthesitis Index at all measured time points as compared to baseline
- Change in mNAPSI at all measured time points as compared to baseline
- Change in PhGA (VAS) at all measured time points as compared to baseline
- Change in Patient's Assessment of PsA Pain Intensity (VAS) at all measured time points as compared to baseline
- Change in PtGA assessments at all measured time points as compared to baseline
- Change in High sensitivity C-Reactive Protein (hsCRP) at all measured time points as compared to baseline
- Minimal disease activity (MDA) at all measured time points
- Change in DAS28-hsCRP at all measured time points as compared to baseline
- PsO endpoints assessed at all measured time points in subjects with a $\geq 3\%$ baseline PsO BSA:
 - PASI 75 and PASI 90 response
 - Change in sPGA clear and almost clear
- EULAR (European League Against Rheumatism) response at all measured time points
- Change in PsARC (Psoriatic Arthritis Response Criteria) at all measured time points as compared to baseline
- Presence of dactylitis (yes/no) at all measured time points
- Change in LDI at all measured time points as compared to baseline
- Change in LEI at all measured time points as compared to baseline
- Change in FACIT-F at all measured time points as compared to baseline
- Change in BASDAI at all measured time points (in subjects with baseline inflammatory spondylitis, based on investigator judgment, in Study 1311.5) as compared to baseline

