Appendix C. Study Activities

		Treatment				Follow-Up		Follow-up Phone Call
		V1	V2	V3	V4	V5 (EOT/Early EOT ^s)	V6	
Week	0^a	4^t	12	24	36	48	52	56
Day	1	29 ± 4	85 ± 4	169 ± 4	253 ± 4	336 ± 4	365 ± 4	392 ± 4
Informed Consent ^b	X							
Inclusion/exclusion criteria	X							
Medical/Surgical History ^c	X ^a							
Patient's Global Assessment of Disease Activity (VAS) (PtGA) ^d	X ^a	X	X	X	X	X	X	
Patient's Assessment of PsA Pain Intensity (VAS) ^d	X ^a	X	X	X	X	X	X	
HAQ-DI ^d	X ^a	X	X	X	X	X	X	
BASDAI ^{d,m}	X ^a			X	X	X	X	
SF-36v2 ^d	X ^a	X	X	X	X	X	X	
FACIT-F ^d	X ^a			X	X	X	X	
Vital Signs ^e	X ^a	X	X	X	X	X	X	
ECG ^e	X ^a			X		X	X	
Physical Exam ^e (c = complete, t = targeted)	X-c ^a	X-t	X-t	X-t	X-t	X-t	X-c	
Concomitant Therapy ^f	X ^a	X	X	X	X	X	X	

	Treatment					Follow-Up	
	V1	V2	V3	V4	V5 (EOT/Early EOT ^s)	V6	EOS (EOT/Early EOT + 16 Weeks)
Week	0^a	4^t	12	24	36	48	52
Day	1	29 ± 4	85 ± 4	169 ± 4	253 ± 4	336 ± 4	365 ± 4
Adverse Event Assessment ^g	X ^a	X	X	X	X	X	X
Tender Joint Count (TJC 68) ^h	X ^a	X	X	X	X	X	X
Swollen Joint Count (SJC 66) ^h	X ^a	X	X	X	X	X	X
PASI ^{h,u}	X ^a	X	X	X	X	X	X
BSA ^h	X ^a	X	X	X	X	X	X
Static Physician's Global Assessment for Psoriasis (sPGA) ^{h,u}	X ^a	X	X	X	X	X	X
Physician's Global Assessment of Disease Activity (PhGA) (VAS) ^h	X ^a	X	X	X	X	X	X
Leeds Dactylitis Index (LDI) ^h	X ^a	X	X	X	X	X	X
Leeds Enthesitis Index (LEI) ^h	X ^a	X	X	X	X	X	X
SPARCC ^h	X ^a	X	X	X	X	X	X
mNAPSI ^h	X ^a	X	X	X	X	X	X
mTSS (X-ray) ⁱ				X	X	X	X
Pregnancy Test ^j	X ^a	X	X	X	X	X	X
Safety Labs (Chemistry, Hematology, Urinalysis) ^{k,v}	X ^a	X	X	X	X	X	X

	Treatment						Follow-Up	
	V1	V2	V3	V4	V5 (EOT/Early EOT ^s)	V6	EOS (EOT/Early EOT + 16 Weeks)	Follow-up Phone Call
Week	0^a	4^t	12	24	36	48	52	56
Day	1	29 ± 4	85 ± 4	169 ± 4	253 ± 4	336 ± 4	365 ± 4	392 ± 4
hsCRP for DAS ^k	X ^a	X	X	X	X	X	X	
Blood Sample for PK ^{k,l}	X ^a	X	X	X	X	X	X	
Blood Sample for ADA Assay ^{k,l}	X ^a	X	X	X	X	X	X	
TB screening ^{k,n}					X		X ^r	
Local tolerability ^o	X	X	X	X	X	X		
Study drug administration	X	X ^p (additional)	X	X	X	X		
Monitoring for hypersensitivity reaction ^q	X	X	X	X	X	X		
Conclusion of Subject participation							X	

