### 10.4 Further Efficacy Analyses

Further efficacy endpoints will include, but are not limited to, the following:

- ACR 50 response at all measured time points in Study M16-244
- ACR 70 at all measured time points in Study M16-244
- Change in Tender Joint Count at all measured time points in Study M16-244 as compared to baseline in Study 1311.5
- Change in Swollen Joint Count at all measured time points in Study M16-244 as compared to baseline in Study 1311.5
- Change in HAQ-DI at all measured time points in Study M16-244 as compared to baseline in Study 1311.5

- Change in SF-36 at all measured time points in Study M16-244 as compared to baseline in Study 1311.5
- Change in Dactylitis count at all measured time points in Study M16-244 as compared to baseline in Study 1311.5 in subjects with dactylitis at baseline
- Change in SPARCC Enthesitis Index at all measured time points in Study M16-244 as compared to baseline in Study 1311.5 in subjects with enthesitis based on SPARCC sites at baseline
- Change in mNAPSI at all measured time points in Study M16-244 as compared to baseline in Study 1311.5
- Change in PhGA (VAS) at all measured time points in Study M16-244 as compared to baseline in Study 1311.5
- Change in Patient's Assessment of PsA Pain Intensity (VAS) at all measured time points in Study M16-244 as compared to baseline in Study 1311.5
- Change in PtGA assessments at all measured time points in Study M16-244 as compared to baseline in Study 1311.5
- Change in High sensitivity C-Reactive Protein (hsCRP) at all measured time points in Study M16-244 as compared to baseline in Study 1311.5.
- Minimal disease activity (MDA) at all measured time points in Study M16-244
- Change in DAS28-hsCRP at all measured time points in Study M16-244 as compared to baseline in Study 1311.5
- PsO endpoints assessed at all measured time points in Study M16-244 in subjects with a  $\geq 3\%$  baseline PsO BSA in Study 1311.5:
  - PASI 75 and PASI 90 response
  - Change in sPGA clear and almost clear
- EULAR (European League Against Rheumatism) response at all measured time points in Study M16-244
- Change in PsARC (Psoriatic Arthritis Response Criteria) at all measured time points in Study M16-244 as compared to baseline in Study 1311.5
- Presence of dactylitis (yes/no) at all measured time points in Study M16-244 in subjects with dactylitis at baseline

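### SAP Table 4 has no Week 4 window for LDI, LEI, SPARCC and mNAPSI, so Week 4 values are not summarised as Week 4 and can be labelled Week 12 when nothing later is available by Day 127

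*SAP*

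**What the plan says.** - **Visits.** Protocol 5.1: "Study visits will occur at Week 0/Enrollment, Weeks 4, 12, 24, 36, 48 and 52". That is seven visits, six of them after baseline.
- **Collection.** In Protocol Appendix C the row beginning "Leeds Dactylitis Index (LDI" carries seven marks, one per visit. The LEI, SPARCC and mNAPSI rows are the same.
- **Endpoints.** Protocol 5.3.3.3 lists "Change in LDI at all measured time points as compared to baseline", and SAP 10.4 repeats the commitment, for example "Change in mNAPSI at all measured time points in Study M16-244 as compared to baseline in Study 1311.5". SAP 10.4 restricts LDI, LEI, SPARCC, dactylitis count and dactylitis presence to subjects with that manifestation at baseline. It puts no such restriction on mNAPSI.
- **Windows.** SAP Table 4, "Analysis Windows for LDI, LEI, SPARCC, mNAPSI During the Open Label Treatment Period", has rows for Weeks 0, 12, 24, 36, 48 and 52 only. Week 12 is Days 2 to 127, target Day 85. Table 1 ("Analysis Windows for Efficacy Variables") and Table 6 (laboratory tests and vital signs) both have a Week 4 row, Days 2 to 57, and start Week 12 at Day 58.
- **Selection within a window.** SAP 6.4: "If more than one assessment is included in a time window the assessment closest to the nominal day will be used". If two are equally distant, the later one is used.
- **Missing data.** SAP 6.5 summarises data as observed and leaves a subject out of a visit's summary when that visit was not evaluated.

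**The concern.** The schedule and the endpoint list point to a Week 4 result for these instruments, and the windowing table leaves nowhere to put it. Three things follow.

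1. The Week 4 summary promised by SAP 10.4 cannot be produced for the four instruments. Dactylitis count and presence come from the same digit examination as the LDI and have no window of their own, so they appear to go with them.
2. Because the Week 12 window opens on Day 2, a Day 29 value can be printed under Week 12 for a subject with no Week 12 evaluation. SAP 6.5 would leave that subject out. Appendix C places clinical assessments before dosing, so in a subject given the optional Week 4 dose the Day 29 value also precedes that dose.
3. Assessments made on the same day can carry different visit labels. On Days 2 to 57 a joint count is Week 4 under Table 1, while an LDI or LEI from that same visit is Week 12 under Table 4.

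**Working it through.** **Step 1: reproduce the SAP's windows.** SAP 6.4 opens the first post-baseline window on Day 2 and splits adjacent visits at the midpoint of their target days. In the SAP's own example and tables, the midpoint day goes to the earlier visit. The last upper bound, 378, is taken as printed.

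| Adjacent targets | Midpoint |
|---|---|
| 29 and 85 | (29 + 85)/2 = 57 |
| 85 and 169 | (85 + 169)/2 = 127 |
| 169 and 253 | (169 + 253)/2 = 211 |
| 253 and 337 | (253 + 337)/2 = 295 |
| 337 and 365 | (337 + 365)/2 = 351 |

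- Without Day 29: 2–127, 128–211, 212–295, 296–351, 352–378. This is Table 4 exactly.
- With Day 29: 2–57, 58–127, then the same. This is Table 1 exactly.

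The omitted Week 4 visit is the whole difference between the two tables.

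**Step 2: apply the closest-to-target rule to the Table 4 Week 12 window (target 85).** A Day 29 value is 85 − 29 = 56 days from target. A later value in the window is at most 127 − 85 = 42 days after the target or, if before it, is nearer than Day 29. So any assessment on Days 30 to 127 displaces Day 29, without exception. The same holds for a Week 4 visit anywhere in its ±4-day range (Days 25 to 33).

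| Pattern of assessments | Value used for Week 12 |
|---|---|
| Days 29 and 85 | Day 85; Day 29 is dropped |
| Day 29, Week 12 missed, Week 24 attended (Day 169) | Day 29 |
| Day 29, then lost to follow-up | Day 29 |
| Day 29, decision to stop on Days 30–84, early end-of-treatment visit within 14 days (Days 30–98) | The end-of-treatment value |
| Day 29, Week 0 dose only, end-of-study visit 16 weeks later: 1 + 112 = Day 113 | Day 113, which is 28 days from target |
| Day 29 with the optional dose, end-of-study visit at 29 + 112 = Day 141 (137–145 with ±4 days), no other visit by Day 127 | Day 29; Day 141 is outside the window |

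**Step 3: size.** The number of stand-in values is the number of subjects with a Week 4 assessment and none on Days 30 to 127. The documents give no missed-visit or dropout rate, so it cannot be computed. For most of these endpoints the denominator is also a baseline subset, not everyone enrolled.

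**Step 4: after the change.** With Week 4 at Days 2–57 and Week 12 at Days 58–127, a Day 29 value is reported as Week 4 and cannot enter Week 12.

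**The case against.** **The schedule may be misread.** The table was read by a program, and some rows show too many marks: mTSS has four against two x-ray time points in the text, and study drug administration has six against five possible doses. The SAP took exactly these four instruments out of Table 1, which would also fit a schedule with no Week 4 mark. This is a sound reason to check the original page. It does not remove the conflict. The four rows are full in the current Appendix C and in both copies in the amendment list, and a truly sparse row such as BASDAI shows fewer than seven marks in each copy.

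**The windowing is prespecified.** SAP 6.4 says that "the first post-baseline interval starts on the first day after the first dose of study drug (Rx Day 2", in order to use all post-baseline data, and Tables 2 and 3 do the same for BASDAI and FACIT-Fatigue. This stands. A reader might call the result an unplanned carry-forward, but it is a stated rule applied to an observed value. What remains is the mismatch with the schedule, with the endpoint wording and with SAP 6.5.

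**Early leavers are mostly covered.** A reader might infer that Week 4 values stand in as Week 12 for subjects who stop early. The documents do not support this. Protocol 5.1 and 5.4.1 ask for an early end-of-treatment visit and an end-of-study visit, Appendix C marks the instruments at both, and any such value on Days 30 to 127 displaces Day 29. The rule for stopping on non-response starts only at Week 12.

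**Week 4 data are not wholly lost.** A Day 29 value is reported when it stands in, though under the wrong label. Enthesitis data may also feed Week 4 MDA, which SAP 10.7.12 derives under the date-by-date ACR logic.

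**Conclusion.** The concern holds in a limited form. If the schedule marks are right, Table 4 is at odds with the protocol schedule and with SAP 10.4. One of six post-baseline summaries is missing for four instruments and apparently for the two dactylitis endpoints. A Day 29 value is labelled Week 12, 56 days early, for subjects with nothing later by Day 127.

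It is tempting to put a count on this by applying an assumed dropout rate to the planned 180 subjects; at 5%, for instance, 0.05 × 180 = 9. The documents give no such rate. That figure would also require every one of those subjects to have no in-window end-of-treatment or end-of-study assessment, and it ignores the baseline subsets. No count should be quoted.

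The consequence is small: these are further endpoints, summarised descriptively without testing, in a study whose primary objective is safety. The conclusion rests on two assumptions: that the seven marks are confirmed on the original schedule page, and that dactylitis count and presence follow the Table 4 windows.

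**What to change.** 1. Check the LDI, LEI, SPARCC and mNAPSI rows on the original page of Protocol Appendix C.
2. If Week 4 is marked, add a Week 4 row to SAP Table 4 (lower bound 2, target 29, upper bound 57) and change the Week 12 lower bound from 2 to 58, matching Tables 1 and 6. State that dactylitis count and presence use the same windows.
3. If Week 4 is left out on purpose, say so and give the reason in SAP 6.4.

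The cost is one added row and one changed bound. No new data are needed, and neither the sample size nor any test is affected. There is one small downside: early end-of-treatment assessments on Days 30 to 57 move from Week 12 to Week 4, as they already do for the Table 1 variables. For that reason the change should not be made by default if Week 4 proves not to have been collected, since the new Week 4 summary could then consist largely of early leavers.

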**Table 5. Analysis Windows for mTSS**

Protocol Specified				
Visit Week		Lower Bound	Target Day	Upper Bound
0 (Study 1311.5)		-999 (Study 1311.5)	1 (Study 1311.5)	13 (Study 1311.5)
24 (Study 1311.5)		14 (Study 1311.5)	169 (Study 1311.5)	Min (306, Last Day (Study 1311.5)
24 (Study M16-244)		2 (Study M16-244)	169 (Study M16-244)	253 (Study M16-244)
48 (Study M16-244)		254 (Study M16-244)	337 (Study M16-244)	420 (Study M16-244)

**Table 6. Analysis Windows for Analysis of Safety Laboratory Tests and Vital Signs**

Protocol Specified Visit Week	Lower Bound	Target Day	Upper Bound
0	1	1	1
4	2	29	57
12	58	85	127
24	128	169	211
36	212	253	295
48	296	337	351
52	352	365	378

**Table 7. Analysis Windows for Local Tolerability During the Open Label Treatment Period**

Protocol Specified Visit Week	Lower Bound	Target Day	Upper Bound
0	1	1	1
4	2	29	57
12	58	85	127
24	128	169	211
36	212	253	295

## 6.5 Missing Data Handling

All data will be summarized as observed, and thus a subject who does not have an evaluation on a scheduled visit will be excluded from the summary for that visit.

